# **OBJECTIVES:**

Diabetes mellitus (DM) poses a significant health burden to pregnant women.  Effective treatment can reduce the risk of adverse maternal and child health outcomes of T2DM and GDM.  However, successfully managing DM in pregnancy is challenging due to the complexity of self-management skills and high level of engagement in health care required for optimal glycemic control. Moreover, pregnancy is considered a window of opportunity for health behavior optimization due to both enhanced motivation and health care access. However, perinatal management of DM requires unique and advanced patient education and engagement. Existing support tools for this critical period of care are currently insufficient to address the identified multitude of logistical, informational, social, psychological, financial, and physical barriers to perinatal management of DM. 

To address these needs, we created a "first-of-its-kind" mHealth platform for pregnant women with GDM or T2DM. This platform, named SweetMama, is a theory-driven application that delivers an interactive, goal-oriented educational and motivational diabetes-focused curriculum.

The next steps include performing usability testing of SweetMama. The aim is to create a refined version of SweetMama via a sequential process of in-depth usability and feasibility testing:

- 1. Focus groups and/or individual user interviews with 10-30 low-income pregnant women with DM to evaluate tool functionality, design, and interpretability.
- 2. Focus groups and/or individual interviews with up to 50 health care providers who serve the patient population to obtain expert feedback and to evaluate SweetMama's clinical usability and feasibility
- 3. Individual usability testing with up to 30 women, who will use SweetMama for 2 weeks followed by qualitative (interviews) and quantitative (questionnaires and user interaction data) assessments of tool satisfaction and use.
- 4. Feasibility testing via a pilot randomized controlled trial (RCT) with up to 50 women in order to determine acceptability, feasibility, and pilot procedures for a fully powered RCT. Providers of patient participants will also provide feedback via surveys and interviews.

# The objectives are to:

- Develop SweetMama and optimize its functionality through laboratory and field usability testing.
- Optimize SweetMama for patient preferences and satisfaction.

• Determine SweetMama feasibility; prepare for and conduct a pilot randomized controlled trial (RCT) comparing SweetMama use to standard of care.

# Secondary aims include:

- Exploration of the mediating effects of adherence markers (e.g. use time, app launches, etc.),
   SweetMama content (e.g. logistical, supportive or educational messaging), and patient characteristics (e.g. demographic, clinical, or self-reported measures).
- Optimize support strategies and content within SweetMama.
- Explore and optimize strategies to incorporate SweetMama into routine clinical care for low-income pregnant women with diabetes. Optimize SweetMama for provider satisfaction and clinical efficiency.
- Determine health care provider perspectives on SweetMama use during feasibility assessments (pilot RCT).

### **BACKGROUND:**

Diabetes mellitus (DM) during pregnancy is a major public health problem. Obesity and DM are serious pregnancy comorbidities with significant maternal and neonatal health implications. Driven by the obesity epidemic, the frequencies of gestational diabetes mellitus (GDM) and type 2 diabetes mellitus (T2DM) have risen significantly, creating a major public health problem. DM has well-established relationships with adverse perinatal outcomes, including cesarean delivery, hypertensive disorders, macrosomia, and neonatal metabolic complications, resulting in short- and long-term decrements in health for both mother and child. DM

Racial/ethnic disparities related to DM in pregnancy exist. Minority women experience pregnancy-related health disparities, including an approximately two-fold greater incidence of GDM, GDM recurrence, and subsequent T2DM after GDM. Over half of women with GDM and over two-thirds of women entering pregnancy with T2DM are from minority racial/ethnic groups. Minority women with DM also experience more frequent adverse perinatal outcomes; for example, non-Hispanic black women with GDM have a greater risk of cesarean delivery, macrosomia, and fetal demise than white women with GDM. The increased prevalence of DM and higher risk for DM-associated adverse outcomes widen existing health disparities.

Treatment of abnormal glucose homeostasis during pregnancy reduces the risk of adverse outcomes. 1,3,25 Care is centered around goals of optimizing glycemic control and monitoring for complications. Multidisciplinary treatment plans include medical nutrition therapy, exercise, potential medication administration, and enhanced maternal-fetal surveillance. 1,2 Thus, perinatal care for DM necessitates advanced patient education and engagement. While pregnancy already requires enhanced patient learning, DM management further complicates perinatal care.

Given the complexity of perinatal DM management, women must be equipped with communication, literacy, numeracy, problem-solving, and organizational skills to optimize outcomes. DM self-management during pregnancy is burdensome and challenging, particularly for women with greater social disadvantage. Logistical, social, financial, informational, access-related, and attitudinal challenges to DM management have been identified in several cohorts and our own data.

While traditional DM behavior support interventions can be effective for non-pregnant adults, scalable interventions that promote sustainable behavior change, address disparities, and are specific to pregnancy are

urgently needed. The expansion of mobile technology has made mobile health ("mHealth") applications a promising avenue for health promotion, especially in DM. Text messages, for example, can be motivators, information sources, cues to action, reminders and reinforcements, and sources of support. Outside of pregnancy, mHealth use is associated with improvements in glycemic control, self-care behaviors, adherence, engagement, self-efficacy and health care costs.

Despite the proliferation of commercial mHealth "apps", evidence-based mHealth interventions for pregnant women are lacking. Interest in such programs is high, with data showing the majority of pregnant women are interested in and have access to mHealth. 40,41 Text4baby, for example, delivers health promotion messages to enhance general pregnancy health behaviors and may positively affect health attitudes. 42-45 Other text messaging programs for reproductive aged women have investigated smoking cessation, contraception, and weight loss. 46 Yet, many programs lack rigorous evidence-based or user-centered design, 31 and advanced or disease-specific perinatal mHealth interventions are lacking. Interventions designed for use by pregnant women with DM, particularly in low-income populations, are needed. 46

To fill this gap, we ENREF 10 initiated a multiphase project to develop a behavioral health intervention to support pregnant women with DM, with particular attention to low-income women. In prior work we developed a model of barriers to self-care and factors that help to overcome these barriers. Yes, 47 We then applied those findings to develop a patient-driven text messaging curriculum to support DM self-care ("Texting for Diabetes Success"), which was performed at NMH within the Prentice Ambulatory Care clinic. The curriculum created for that program serves as the backbone for SweetMama. Participants reported high satisfaction and perceived benefits from this curriculum, and desired that we extend it further with interactive and individualized features. Based on these findings, we created SweetMama, a supportive and educational theory-driven mHealth platform for pregnant women with GDM or T2DM. SweetMama delivers an interactive, goal-oriented educational and motivational diabetes-focused curriculum. Our long-term hypothesis is that use of a high quality mHealth tool can improve maternal glycemic control, positively impact maternal and neonatal outcomes, and thus contribute to reducing perinatal DM-related disparities.

Finally, effective perinatal mHealth interventions require a theoretical framework to derive the greatest benefit. 32,46 The Health Belief Model explains individuals' engagement in health behaviors via the constructs of perceived susceptibility, severity, barriers, and benefits. 48 Cognitive load refers to a task's cognitive demand 49,50 and suggests individuals have a limited capacity to process information. 51-53 The learning and decision making burdens of DM management demand self-efficacy, confidence in the ability to perform a particular set of behaviors. 54 DM self-efficacy is particularly salient in pregnancy, where in a short amount of time a woman must believe she can accomplish new health behaviors in order to successfully execute those changes. 55 We have applied these theories in the development of SweetMama.

SweetMama currently functions as a user-friendly application in which participants are delivered three library-based messages per week, in which messages derive from the previously-developed and newly expanded curriculum, and one individualized goal-based message that is customized to the patient. All messages designed as dynamic messages that allow for receipt of novel educational, motivational, or supportive content when desired by patients. Messages can be "favorited" and archived, and can be viewed on WiFi or when outside of data/WiFi capacity. The intervention is designed to be a simple but consistent plan of supportive and reinforcing messages that promote self-efficacy, engagement, and knowledge during a pregnancy complicated by diabetes. We have previously tested and utilized the primary messaging content in the Texting

for Diabetes Success study, and have now expanded both the content as well as transitioned from simple texting to smartphone-based technology. Modification of SweetMama throughout the early phases of this investigation have resulted in improvements in the curriculum, algorithm for curriculum delivery, graphics, and user-friendliness of the intervention.

Although the technology has been tested with our core group of expert users, further provider feedback in addition to in-depth user testing will allow for app optimization prior to a large-scale trial on the relationship between SweetMama use and perinatal outcomes.

Thus, this proposal will solicit in-depth user-centered feedback on SweetMama, allowing us to iteratively modify SweetMama. At each phase of usability and feasibility testing, we are making modifications that improve SweetMama and generate insight into the ability to conduct a larger randomized controlled trial to assess clinical outcomes. Accomplishment of usability phases will result in an optimized tool ready for longitudinal field testing via a pilot randomized controlled trial, which is the current stage of feasibility testing.

# **INCLUSION AND EXCLUSION CRITERIA:**

Inclusion criteria

Patient focus groups and individual user testing:

- Age 18 and greater
- Gestational diabetes mellitus or type 2 diabetes mellitus
- English-speaking (as SweetMama currently does not exist for non-English speakers)
- Gestational age:
  - Focus groups and individual user interviews: Confirmed intrauterine pregnancy at least 8 weeks' gestational age or postpartum until 12 weeks after delivery
  - Individual testing: Pregnant with a confirmed intrauterine pregnancy at least 6 weeks' gestational age, up to 4 weeks postpartum
  - Pilot randomized trial: Pregnant women with a confirmed intrauterine pregnancy (at least 6 weeks' gestational age) who are initiating diabetes care at the study site and are less than 30 weeks' gestational age. Enrollment will be permitted until 30 weeks as data show even late treatment can improve DM-associated outcomes.
- Patient at Prentice Ambulatory Care, General Obstetrics/Gynecology, or Maternal-Fetal Medicine practices at Northwestern Medicine
- Low income, defined as use of publicly-supported insurance for prenatal care or household income
   <200% of poverty line for family size

- Access to a smartphone (for longitudinal testing phases)

# Health care provider testing:

- Practicing MD (resident, fellow, or faculty), nurse, diabetes educator, lactation consultant, medical assistant, patient services representative, or registered dietitian within Prentice Ambulatory Care/ Maternal-Fetal Medicine at Northwestern Medicine
  - Pilot randomized trial: Provider must be caring for a patient enrolled in the pilot randomized trial.
- Age 18 or greater

English-speaking

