# Exclusion criteria:

- Failure to meet the inclusion criteria above
- Patient aims: Non-viable pregnancy

Maximum total number of participants: 180

- 10-30 women to participate in focus groups and individual user interviews
- Up to 30 women to participate in individual field testing
- Up to 50 health care providers to provide expert feedback in focus groups and interviews
- Up to 50 women to participate in the pilot RCT
- Up to 30 health care providers to participate in surveys and interviews affiliated with the pilot RCT

We will specifically include pregnant women as pregnancy is a requirement for participation; the goal of the study is to develop a tool for use by pregnant women. This study does not include adults unable to consent, minors, or prisoners.

STUDY-WIDE NUMBER OF PARTICIPANTS: Not applicable, not a multi-center study

STUDY-WIDE RECRUITMENT METHODS: Not applicable, not a multi-center study

**MULTI-SITE RESEARCH:** Not applicable

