- Treatment adherence, measured as 1) retention in clinical care with completion of all recommended selfcare measures (visits attended and with glucose data available), and 2) proportion of glucose values out of range when presenting to care
- Maternal and neonatal outcomes, including glycemic control (Appendix A)

For the SweetMama arm, we will collect unique data on:

- Quality assurance and technical functioning: At each technical check-in point, we will complete a short standardized check-in regarding any errors, technical problems, or content clarifications. In this field testing phase, the 2-item quality assurance check-in will be completed by completion of a brief mobile REDCap survey.
- Interview Semi-structured interview framed by the Health Belief Model on experiences with SweetMama. Information will be designed to elicit feedback about technical problems, ease of use, satisfaction abd overall usefulness for various components of SweetMama (see Appendix F)
- Satisfaction measured via the System Usability Scale (SUS).
- Satisfaction and usability measured via the Usefulness, Satisfaction and Ease of Use (USE)
   Questionnaire
- User interaction data client event data will be identical to data in the usability phase.

[figure not shown]
As in the usability phase, only data related to how and when SweetMama is used will be collected and the format in which it is stored will contain no identifying information about users. Furthermore, the information saved on the server will only be accessible to people provided with the proper credentials (members of the research team, research collaborators, and the users themselves). All study activities will take place within Northwestern Medicine, specifically in the PAC clinic, General Obstetrics/Gynecology practice, and Maternal-Fetal Medicine practice. No physical procedures will be performed and there are no specific procedures used to monitor participants for safety or minimize risks, as this poses no more than minimal risk to participants. Source records for the study include interviews, surveys, and chart data, as described above. All questionnaires will be collected using REDCap. The study has been updated in clinicaltrials.gov per requirements.

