# Feasibility testing: Pilot RCT (clinician phase)

Clinicians will be recruited using similar processes as described above for the clinician focus group phase. These stakeholders (nurses, physicians, nurse practitioners) will be individuals who care for enrollees in the pilot randomized trial, including both those who are SweetMama users and those receiving usual care. Providers will not be asked any personal questions about themselves. There will be three brief phases of provider enrollment:

- Upon patient participant enrollment, their primary provider will undergo a brief REDCap-based survey regarding perceptions of patient engagement in general, using an adapted version of the Clinician Support for Patient Activation (CSPAM) measure. The 14-item CSPAM addresses how far clinicians value people's role in the care process and indicates clinician level of endorsement about the importance of patient activation. This measure assesses a stable characteristic about a provider and thus will only be asked once. Additional questions will address their expectations for SweetMama involvement. At this point, the provider will also be provided brief education about SweetMama's goals and their involvement in the goal-setting component.
- Upon patient participant completion, providers will undergo a brief follow-up survey regarding their individual patient's engagement and adherence. Questions will be modified from the CSPAM and additional items will specifically query their opinions about SweetMama. Providers will complete this brief survey for each participant.
- Upon patient participant completion, providers will be asked to undergo a single in-depth interview.
   The qualitative interview will address if and how SweetMama affected provider roles, whether and how providers perceived benefit, and future suggestions. If a provider cared for multiple patients who used SweetMama, she will be asked to reflect on each individual participant's engagement as well as overall perspectives on the program.

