#### **SETTING:**

This project will include participation of the clinic staff and patients. Clinics to serve as study sites include the Prentice Ambulatory Care (PAC) clinic, and the Northwestern Medicine Group Maternal-Fetal Medicine practice and the General Obstetrics/Gynecology practice. The focus of this work is to improve care for low-income women with diabetes during pregnancy, the majority of whom receive care in the PAC clinic. All patients deliver at Prentice Women's Hospital, a tertiary care, referral center.

The study will also take place at the Center for Behavioral Intervention Technology, a unique Northwestern core facility with extensive research expertise who have been key partners in this study. No research activities are taking place outside of Northwestern.

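### Pilot provider eligibility omits General Obstetrics/Gynecology, although the pilot recruits women there and surveys each enrollee's primary provider

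*Combined protocol and SAP*

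**What the plan says.** All references are to the current protocol, the later of the two in the combined document.

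- **Provider eligibility** (Inclusion and Exclusion Criteria, Health care provider testing). The role list opens "Practicing MD (resident, fellow, or faculty), nurse, diabetes educator, lactation consultant, medical assistant, patient services representative" and closes "or registered dietitian within Prentice Ambulatory Care/ Maternal-Fetal Medicine at Northwestern Medicine". Nested beneath it is a condition for the pilot: "Pilot randomized trial: Provider must be caring for a patient enrolled in the pilot randomized trial".
- **Exclusion criteria.** The first entry is "Failure to meet the inclusion criteria above".
- **Patient eligibility** (Inclusion and Exclusion Criteria). Women qualify by practice as "Patient at Prentice Ambulatory Care, General Obstetrics/Gynecology, or Maternal-Fetal Medicine practices at Northwestern Medicine".
- **Pilot activity sites** (Feasibility testing: Pilot RCT, patient component). Activities take place "specifically in the PAC clinic, General Obstetrics/Gynecology practice, and Maternal-Fetal Medicine practice".
- **Setting.** The study clinics include the "Maternal-Fetal Medicine practice and the General Obstetrics/Gynecology practice".
- **Pilot clinicians** (Feasibility testing: Pilot RCT, clinician phase). "These stakeholders (nurses, physicians, nurse practitioners) will be individuals who care for enrollees in the pilot randomized trial", in both arms. When a woman enrols, her primary provider completes an entry survey. The same section asks for an exit survey for each participant and one interview per provider.
- **Aim.** Provider perspectives on SweetMama during the pilot are one of the secondary aims.

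**The concern.** The set of practices that supplies women to the pilot is wider than the set that may supply provider participants. Where a woman's primary provider works only in General Obstetrics/Gynecology, study staff have two incompatible instructions. They can survey that provider, as the clinician-phase section directs, and enrol someone who fails the written criteria. Or they can apply the criteria and leave that woman's provider data uncollected.

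The second course would lose data by practice, not at random. Provider feedback would then come from Prentice Ambulatory Care and Maternal-Fetal Medicine only, although another secondary aim is to learn how SweetMama can be incorporated into routine care.

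**Working it through.** No arithmetic underlies the inconsistency, so the check is to set the sections side by side.

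1. **Does the pilot condition open a separate route in?** It sits as a sub-item under the role-and-practice criterion. Its natural reading is an added requirement: the provider must have a listed role, work in a listed practice and, for the pilot, also be caring for an enrollee. It does not waive the practice limit.
2. **Is the practice limit operative?** Yes. Because failing an inclusion criterion is itself an exclusion, leaving out General Obstetrics/Gynecology has the effect of excluding it, although no sentence says so expressly.
3. **Is General Obstetrics/Gynecology really part of the pilot?** Three current places say so: patient eligibility, the pilot activity sites and Setting. The activity-site sentence for individual usability testing names only the other two practices, and the pilot sentence adds this one.
4. **Do the pilot procedures limit providers by practice?** No. The clinician-phase section defines them by whom they care for. The Procedures section likewise speaks of up to 30 providers of enrolled participants, with no practice named.
5. **Does any current section extend the provider criteria?** None was found.

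Hence the eligibility criteria and the clinician-phase section conflict for clinicians based solely in General Obstetrics/Gynecology. A clinician who also works in either listed practice can still qualify, because the criteria do not require exclusive practice.

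**How many women?** This cannot be calculated. The pilot targets 40 women, with up to 50 allowed, and no split by practice is given. Recruitment Methods says only that the majority of patients will come from Prentice Ambulatory Care. If that also holds within the pilot (an assumption, since the statement covers the whole study):

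- at 40 women, a majority is at least 21, leaving at most 40 − 21 = 19 for the other two practices combined;
- at 50 women, a majority is at least 26, leaving at most 50 − 26 = 24.

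These are loose ceilings. They include Maternal-Fetal Medicine, whose providers are eligible, and women in General Obstetrics/Gynecology whose provider also works in a listed practice.

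**Roles.** The clinician-phase section names nurses and nurse practitioners separately, while the eligibility list names only nurse. The broader word can be read to cover both, so this is an ambiguity and not a demonstrated exclusion.

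**The case against.** The best defence is that the intended scope is plain. Both operational sections describe pilot providers as those caring for enrollees, and the change summary for version 8 says the same. The eligibility line looks as though it was simply not updated when the practice was added for patients. The aim affected is secondary, provider surveys are to be summarised descriptively, participation is voluntary, and complete provider data for each practice was never promised. All of this stands, and it keeps the point small. It does not remove the conflict, because eligibility criteria are the operative rule for enrolment and staff should not have to infer an exception.

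Three stronger readings are tempting, and the documents do not support them.

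- **That women in General Obstetrics/Gynecology would lose provider goal-setting.** The criteria govern who may be a research participant, not who may deliver care or be educated. Goals are chosen with the clinical team at appointments, and no section makes this conditional on a clinician's enrolment. Provider education is timed with the entry survey but is not restricted to eligible providers.
- **That no woman from that practice would have provider data.** This would require that none of its clinicians also works in Prentice Ambulatory Care or Maternal-Fetal Medicine, which the documents do not say.
- **That a particular number of women is affected.** Any such figure would rest on an assumed share with no source in the documents.

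**Conclusion.** The inconsistency is real and minor. As written, clinicians who work only in General Obstetrics/Gynecology cannot be enrolled as pilot provider participants, although women are recruited from their practice and the procedures call for each enrollee's primary provider to be surveyed. The consequence is selective loss of one practice from a secondary, descriptive aim. The number of women concerned is unknown and probably a minority.

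The conclusion rests on two things: reading the pilot condition as an addition to the practice limit, and there being at least one primary provider based solely in General Obstetrics/Gynecology. If every such provider also works in a listed practice, nothing is lost in practice and only the wording needs repair. Randomisation, retention, satisfaction and the clinical outcomes are not touched.

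**What to change.** In the provider eligibility criteria, for the pilot, add General Obstetrics/Gynecology to the listed practices, so that a provider caring for an enrollee is eligible whichever of the three practices she attends. In the same edit, state that nurse includes the nurse practitioners named in the clinician-phase section.

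The cost is a one-line eligibility amendment. The cap of 30 pilot providers, the survey instruments and the analysis plan can stay as they are.
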